8.1.3 Sample Size Considerations

With a 2-sided significance level of 0.05, a sample size of 152 in each group would be required to detect a 2 mm difference in IOP with 80% power (accounting for a 10% drop out rate). The total planned enrollment for this pilot study is approximately 304 subjects

8.1.4 Statistical Methods

Descriptive statistical analysis of patient characteristics across the 2 treatment groups will be performed. Snellen VA measurements will be converted to logMAR equivalents for the purpose of data analysis. Student t test for continuous variables, Fisher exact test, and the χ^2 test, or exact permutation χ^2 test for categorical variables will be utilized. All tests will be 2-sided in accordance with our hypothesis. A P-value of 0.05 will be considered statistically significant.

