2.0 STUDY FLOW CHART

| | | | Study Day | | | | | |
|---|----------------------------|-----------------------|-------------------------|-------------------------|-------------------------|--------------------------|---------------------------|--------------------------|
| | | | | | | | | |
| | Screening / Baseline visit | Post-Op Day 1 ± 1 day | Post-Op Week 1 ± 5 days | Post-Op Week 4 ± 1 week | Post-Op Week 6 ± 1 week | Post-Op Month 3 ± 1 week | Post-Op Month 6 ± 2 weeks | Post-Op Year 1 ± 1 month |
| Informed Consent | X | | | | | | | |
| Review inclusion and exclusion criteria | X | | | | | | | |
| Visual acuity assessment | X | X | X | X | X | X | X | X |
| Slit-lamp biomicroscopy | X | X | X | X | X | X | X | X |
| Applanation Tonometry | X | X | X | X | X | X | X | X |
| Subjective diplopia | | X | X | X | X | X | X | X |
| Pachymetry | X | | | | | | | X |
| Direct fundus exam | X | | | | | | | X |
| Humphrey visual field | X | | | | | | | X |
| Optical coherence tomography | X | | | | | | | X |
| Self-report dysesthesia scale | X | | | | | | | X |
| Motility history and exam | X | | | | | | | X |
| Quality of life questionnaires | | | | | | | | X |

X procedure performed at the time of clinic visit

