5.3 Sample Size

Approximately 152 subjects will be enrolled in each treatment group for a total of approximately 304 subjects. This sample size was based on a power analysis aimed at detecting a 2 mmHg difference in IOP between the Baerveldt and ClearPath groups with 80% power, using the mean post-op year 1 Baerveldt IOP of 13.6 ± 5.9 mmHg from the pooled AVB and ABC data.⁴ The results were adjusted for an expected 10% drop out rate at 1 year.

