5.5 Study Evaluation

If the potential subject meets the criteria for study-inclusion and consents to participate following full explanation of the research, the subject will be randomly assigned to either group. The subject's baseline exam findings will be documented, including: age, sex, race, glaucoma diagnosis and cause, ocular history (including prior treatments and procedures), best-corrected Snellen visual acuity, IOP by Goldmann applanation tonometry (masked, 2-person), glaucoma medications, slit lamp findings, external exam findings, motility exam, Humphrey Visual Field, Optical Coherence Tomography, and a patient reported-reported dysesthesia scale.

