5.6 Randomization and Masking

At the time of consent, subjects will be randomized to receive either the Baerveldt or ClearPath according to a computer-generated randomization code. Study subjects will be masked as to which implant they will receive. In the patient chart, the device will be noted at a glaucoma drainage device (GDD).

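### The year-1 IOP comparison is planned as an unadjusted Student t test; ANCOVA on the baseline IOP already being collected would be at least as precise in practice, at almost no cost

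*Combined protocol and SAP*

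**What the plan says.** Section 8.1.4 is the whole statement of statistical methods. For continuous outcomes it gives "Student t test for continuous variables"; the other tests it lists are for categorical variables. No ANCOVA, regression, mixed model or covariate appears anywhere. Section 8.1.1 adds only the ITT population, LOCF and the handling of rescue procedures.

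The trial was sized on IOP. Section 5.3 bases the calculation on the raw year-1 value, "using the mean post-op year 1 Baerveldt IOP of 13.6 ± 5.9 mmHg", and sets the target at 2 mmHg between the arms. Section 8.1.3 repeats the result: "a sample size of 152 in each group would be required to detect a 2 mm difference in IOP with 80% power".

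Baseline IOP is collected with care. Section 5.5 lists "IOP by Goldmann applanation tonometry (masked, 2-person" among the baseline findings, and the flow chart in Section 2.0 marks applanation tonometry at the baseline visit and every later visit. Its only stated use in an outcome is the 20% reduction criterion for device failure in Section 3.2, which is a separate binary outcome.

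Section 5.6 says that subjects are randomized "according to a computer-generated randomization code". It mentions no stratification, by baseline IOP or by anything else.

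**The concern.** A two-group t test on the year-1 value leaves in the residual whatever part of the variation baseline IOP could explain. If the two measurements are correlated, three things follow.

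- **Precision.** The confidence interval is wider than the same data could give. This matters here because Section 3.2 expects no difference between the devices. The width of the interval then largely decides what a null result tells surgeons.
- **Chance imbalance.** With no stated stratification by baseline IOP, any imbalance between the arms passes into the unadjusted estimate in proportion to r.
- **Pre-specification.** If no covariate is named now, a later adjusted analysis will be open to the charge that it was chosen after the results were seen.

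**Working it through.** **Inputs**

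- Two-sided alpha 0.05 (Section 8.1.3)
- Difference 2 mmHg, power 80%, SD 5.9 mmHg, dropout 10% (Section 5.3)
- Correlation r of baseline with year-1 IOP: not in the documents. Assumed range 0 to 0.5.

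**Step 1: reproduce the plan's figure.** By the normal approximation, n per arm = 2 × (1.960 + 0.842)² × 5.9² / 2² = 136.6, so 137. Allowing for dropout, 137 / 0.9 = 152.2, which agrees with the stated 152. The calculation uses the SD of the raw year-1 value and no baseline information.

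**Step 2: the planned t test at 137 evaluable per arm.** SE = 5.9 × √(2/137) = 0.713 mmHg. The noncentrality is 2 / 0.713 = 2.81 with 272 df, which gives 79.8% power. The 95% CI half-width is 1.969 × 0.713 = 1.40 mmHg.

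**Step 3: ANCOVA on baseline IOP.** The residual SD is 5.9 × √(1 − r²). ANCOVA's own cost is included: one degree of freedom (271 df) and an expected variance inflation of 1 + 1/270 for chance imbalance in the covariate.

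**Step 4: effect of chance imbalance on the t test.** The baseline difference between arms has an SD of √(2/137) = 0.121 baseline SDs. An imbalance of that size shifts the unadjusted difference by r × 5.9 × 0.121.

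| r | Residual SD (mmHg) | ANCOVA power | ANCOVA 95% CI half-width (mmHg) | Shift in unadjusted difference (mmHg) |
|---|---|---|---|---|
| 0 | 5.90 | 79.7% | 1.41 | 0 |
| 0.1 | 5.87 | 80.1% | 1.40 | 0.07 |
| 0.2 | 5.78 | 81.3% | 1.38 | 0.14 |
| 0.3 | 5.63 | 83.3% | 1.34 | 0.21 |
| 0.4 | 5.41 | 86.1% | 1.29 | 0.29 |
| 0.5 | 5.11 | 89.7% | 1.22 | 0.36 |

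Against 79.8% and 1.40 mmHg for the t test, ANCOVA loses about 0.1 point at r = 0. It gains 1.5 points at r = 0.2, 3.5 at r = 0.3 and 9.9 at r = 0.5.

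**Step 5: is a t test on change from baseline an alternative?** Assume an SD of 5.9 at both times. The SD of change is then 5.9 × √(2(1 − r)), which is 8.34 at r = 0, 6.98 at r = 0.3 and 5.90 at r = 0.5. Power at 137 per arm is about 51%, 66% and 80%. Under this assumption, change from baseline is worse than the raw year-1 value for any r below 0.5, and worse than ANCOVA throughout the range.

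**The case against.** The strongest objection is that the benefit rests on a correlation that the documents do not supply and that may be low. Enrolment is restricted to inadequately controlled glaucoma (Section 6.1). Added medication, ripcord removal and further surgery are at the surgeon's discretion (Section 7.2). Nothing in the documents supports an r of 0.3 to 0.5. This stands: the size of the gain is unknown and could be negligible. It does not defeat the recommendation, because the downside is bounded at about 0.1 point.

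Second, the plan never says in words whether the t test is applied to the year-1 value or to the change, and Section 3.2 speaks of IOP reduction. That is fair. Section 5.3 points to the year-1 value, because both the mean and the SD are of that value. If change were meant, baseline IOP would be used, but less efficiently than by ANCOVA (Step 5).

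Third, under ITT with LOCF the number analysed may be nearer 152 than 137 per arm. If the SD stays at 5.9, the t test then has 83.8% power and a half-width of 1.33 mmHg. ANCOVA has 83.7% at r = 0, 85.1% at r = 0.2, 86.9% at r = 0.3 and 92.4% at r = 0.5. The gains become about 1.3, 3.1 and 8.6 points and the worst case is still about 0.1 point, so the comparison of methods hardly changes.

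Fourth, chance imbalance is the same loss of precision seen conditionally, and the t test's interval already allows for it. That is correct on average over randomizations; the shifts in the table lie well inside 1.40 mmHg and are not a separate bias. Likewise, the plan names only one test, so it offers no choice between results. The value of naming the covariate now is that adjustment could not be added credibly later.

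**Conclusion.** The concern holds. Section 8.1.4 commits the year-1 IOP comparison to an unadjusted t test and leaves unused a baseline value scheduled for every subject. The planned analysis is valid and consistent with its sample size; what is lost is efficiency. At 137 per arm, adjusting changes power by about −0.1 point at r = 0, +1.5 at r = 0.2 and +3.5 to +9.9 for r of 0.3 to 0.5. The half-width falls from 1.40 to between 1.34 and 1.22 mmHg over that last range. These figures rest on the protocol's SD of 5.9, an assumed r, and a linear relation between baseline and year-1 IOP that is the same in both arms. The change should be made, but the plan is not unsound without it.

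**What to change.** Add to Section 8.1.4, before outcome data are compared by arm:

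> The primary comparison of year-1 IOP is an ANCOVA with device and baseline IOP as terms, reported as the adjusted difference with its 95% CI. The Student t test is supportive.

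This wording also fixes the tested variable as the year-1 value and calls that comparison primary. Section 8.1.1 refers to a primary efficacy analysis without naming its variable, so the investigators should confirm that this is what they intend.

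The cost is one sentence. No new data are needed, and the sample size and the population and data-handling rules in 8.1.1 stay as they are. If baseline IOP turns out to be uninformative, about 0.1 point of power is lost.

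Surgeon may be added in a sensitivity analysis, as a random effect or with low-volume surgeons pooled. It should not be a many-level fixed factor in the primary model, because stratification by surgeon is not stated. Assuming 14 equal-volume surgeons, unstratified allocation and no true surgeon effect, simulation gives a mean variance inflation of 1.05. Power with surgeon plus baseline IOP is then 77.7% at r = 0 and 79.3% at r = 0.2, below the plain t test.

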3.2 Rationale

Previous studies have compared the efficacy of the Baerveldt to the older, valved Ahmed FP7 glaucoma drainage device (Ahmed Glaucoma Valve; New World Medical, Inc., Rancho Cucamonga, CA). These studies have yielded mixed results, and many surgeons will opt to use either a Baerveldt or an Ahmed FP7 depending on a number of patient-dependent factors. However, there is currently no data published comparing the Baerveldt to the new, non-valved Ahmed ClearPath. We are interested in performing a head-to-head trial in order to compare overall efficacy and failure rates of the Baerveldt as compared to the ClearPath. Criteria for device failure includes: IOP $> 18 \text{ mmHg}$ or not reduced by 20% less than baseline on two consecutive visits after three months, IOP $< 6 \text{ mmHg}$ on two consecutive visits after three months, need for additional glaucoma surgery or device removal, and the loss of light perception vision. Given the similarities in design, in particular the equal sizes of the implant plate, we hypothesize that there is no difference in the efficacy of IOP reduction or complication rates in patients who undergo Baerveldt implant versus those who undergo ClearPath implants. However, this cannot be verified without sufficient investigation. The results of this study will provide important data for surgeons to select the most appropriate device to achieve favorable outcomes while minimizing complications.

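### Failure rates are an aim, but the plan lists only tests of proportions and LOCF, so early dropouts would in effect count as not failed; a time-to-failure analysis is a cheap improvement

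*Combined protocol and SAP*

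**What the plan says.** - **Aim.** Section 3.2 (Rationale) states the intent to "compare overall efficacy and failure rates of the Baerveldt as compared to the ClearPath". It lists the failure criteria: IOP too high, insufficiently reduced or too low at two visits in a row once three months have passed; further glaucoma surgery or device removal; and loss of light perception.
- **Hypothesis.** Section 8.1.2 names IOP and complication rates. It does not name failure.
- **Tests.** Section 8.1.4 gives the t test for continuous variables and, for the rest, Fisher, chi-square or an "exact permutation χ^2 test for categorical variables". No Kaplan-Meier, log-rank or Cox method appears anywhere.
- **Missing data.** Section 8.1.1 applies LOCF in the primary efficacy analysis, to randomised subjects seen at least once after surgery. It mentions failed surgery only to fix which value is used after a rescue procedure.
- **Dropout.** Section 5.3: "The results were adjusted for an expected 10% drop out rate at 1 year".
- **Visits.** From three months on, the scheduled visits are month 3, month 6 and Year 1 (sections 2.0 and 7.2). Extra appointments are allowed when needed.

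**The concern.** Failure happens at different times, and some subjects will leave before their status at one year is known. A test of proportions needs a yes or no for everyone, so each early leaver must be classed as not failed, classed as failed, or left out. The plan does not choose.

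If LOCF is applied to failure status, the choice is made by default. Anyone who leaves before month 6 cannot have met the two-visit IOP criterion on scheduled visits. If the month 3 visit does not count as being after three months, anyone who misses Year 1 is in the same position. Unless they failed on another criterion first, they are carried forward as not failed.

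This lowers the reported failure rate in both arms. If dropout differs between arms, the arm that loses more subjects looks better. Unequal or outcome-related dropout is possible here: surgeons are not masked (section 5.1), further surgery is at their discretion (section 7.2), and withdrawal may follow adverse effects or an investigator's request (section 9.5).

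**Working it through.** **1. The plan's own figure.** Section 5.3 describes "a power analysis aimed at detecting a 2 mmHg difference in IOP between the Baerveldt and ClearPath groups with 80% power". The SD is 5.9 mmHg, taken from the published Baerveldt results that the section cites. Per arm, n = 2 × [(1.960 + 0.842) × 5.9 / 2]² = 136.6, and 136.6 / 0.9 = 151.8. The planned 152 per arm reproduces. It is sized on mean IOP, so it is not affected by what follows.

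**2. Inputs for the check.** From the documents: 152 per arm, 10% dropout, two-sided 0.05. Assumed, because the documents give no figure: a true one-year failure rate of 20% in both arms, and, for the unequal case, dropout of 5% vs 15%.

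**3. Failure and dropout spread evenly over the year (constant hazards).** Let λf = −ln(1 − 0.20) = 0.2231 and λd = −ln(1 − dropout). The proportion seen to fail before leaving is λf/(λf + λd) × [1 − exp(−(λf + λd))].
- 10% dropout: λd = 0.1054, giving 0.2231/0.3285 × (1 − 0.80 × 0.90) = 0.679 × 0.28 = 19.0%.
- Leaving out those who drop out without failing: 0.190/(0.190 + 0.72) = 20.9%.
- 5% dropout: 0.2231/0.2744 × 0.24 = 19.5%.
- 15% dropout: 0.2231/0.3857 × 0.32 = 18.5%.
- Spurious difference: 1.0 percentage point.

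**4. Failure declared only at Year 1.**
- 10% dropout: 0.20 × 0.90 = 18.0%.
- 5% vs 15%: 0.20 × 0.95 = 19.0% vs 0.20 × 0.85 = 17.0%, a spurious 2.0 points.

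**5. Simulation.** 152 per arm, 2,000 runs per scenario, three timings of failure: spread over the year, half at month 6 and half at Year 1, or all at Year 1.

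| Assumed scenario | Dropouts as not failed | Dropouts left out | Kaplan-Meier / log-rank |
|---|---|---|---|
| Estimate; true 20%, dropout 10% in both arms | 18.0% to 19.0% | 20.0% to 20.9% | about 20.0% |
| Type I error; true 20% in both arms, dropout 5% vs 15% | 5.3% to 7.8% | 4.7% to 5.3% | 4.6% to 5.2% |
| Power, 10% vs 20%, dropout 10%, failures spread over the year | 65% | 66% | 66% |
| Power, 20% vs 30%, same | 49% | 49% | 50% |
| Power, 20% vs 35%, same | 81% | 81% | 81% |

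Simulation error is about 0.5 points near 5% and 1.1 points near 50%.

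**6. Check on the 7.8%.** For 19% vs 17%, the standard error is √[(0.19 × 0.81 + 0.17 × 0.83)/152] = 4.4 points, so the shift is 2.0/4.4 = 0.45 standard errors. The two-sided rejection rate is Φ(−1.96 + 0.45) + Φ(−1.96 − 0.45), about 7.4%. That agrees with the simulated 7.8% within simulation error.

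**The case against.** **The plan never says that failure will be tested by chi-square or Fisher.** A reader might infer that it does. Section 8.1.4 speaks of categorical variables in general, and section 8.1.2 does not name failure. This stands. Using these tests is the natural reading, since failure is a yes/no outcome and nothing else is listed. If that reading is rejected, a stated aim has no specified analysis, and the remedy is the same.

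**The plan does not say that dropouts are discarded.** A reader might infer this too. By rule, only subjects never assessed after surgery leave the analysis set. LOCF also does not turn every dropout into a success, because someone who failed before leaving would keep that status. Both points stand. The concern is limited to those who leave before failure can be confirmed.

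**The 2-point case does not favour survival methods.** If failure can be declared only at Year 1, every dropout is censored before any event, and Kaplan-Meier equals the completers' proportion. This stands: that case argues against coding dropouts as not failed, not against chi-square as such.

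**The effect is small.** A spurious 1-point difference compares with a standard error of √(2 × 0.20 × 0.80/152) = 4.6 points. The highest type I error needs threefold unequal dropout, and a completers-only chi-square also held its level. This stands and limits the weight of the point. Completers-only still overstates the rate by up to about 1 point and wastes partial follow-up.

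**The change is not free.** Log-rank and Kaplan-Meier assume non-informative censoring, which the withdrawal reasons in section 9.5 put in doubt. IOP failure is seen only at visits, and no section says that failure dates are recorded. This stands: the cost is low, not zero.

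**Conclusion.** The point holds as a cheap improvement to a stated aim. On the natural reading of sections 8.1.1 and 8.1.4, subjects who leave before the two-visit IOP criterion can be confirmed are in effect counted as not failed.

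With an assumed 20% failure rate and the plan's 10% dropout, failure is understated by about 1 to 2 points. With assumed dropout of 5% vs 15%, a spurious difference of about 1 point arises (2 points if failure can be declared only at Year 1), and a nominal 5% test can reject in up to about 8% of trials. With balanced dropout, type I error is not inflated in the simulation.

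Two stronger conclusions are not supported. The trial does not lose meaningful power for want of a log-rank test, since the gain is about 1 point or less in every scenario run. The IOP comparison that sets the sample size is not affected.

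**What to change.** In section 8.1.4, before results are seen:

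- Name failure as an analysed outcome, measured as time from surgery to failure.
- Date the event at the visit that confirms the two-visit IOP criterion, or at the date of further glaucoma surgery, device removal or loss of light perception, whichever comes first.
- State whether the month 3 visit can be the first of the two, and whether nominal or actual visit dates are used. The Year 1 window is ± 1 month, so a curve read at exactly 12 months could miss failures confirmed later in the window.
- Censor subjects without failure at the last assessed visit, and do not apply LOCF to failure status.
- Report Kaplan-Meier one-year failure per arm, with the difference and 95% CI, and compare arms by log-rank.
- Add a sensitivity analysis that counts dropouts as failures. Present it as a bound, not an estimate: under the assumptions of working step 3, 5% vs 15% dropout would give 1 − 0.80 × 0.95 = 24% vs 1 − 0.80 × 0.85 = 32% with no true difference.
- Keep Fisher and chi-square for baseline categories and single-visit outcomes.

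**Cost.** SAP wording, a little programming, and a case report form field for the failure date and reason. No subjects or visits are added. The SAP should state the non-informative censoring assumption and that IOP failures are detected only at visits.

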9.0 HUMAN SUBJECT PROTECTION

9.1 Safety and Confidentiality

No long-term safety concerns are anticipated as a result of study interventions as both devices are FDA approved. The surgeon and his/her study staff will monitor safety events on a regular basis. After-hours contact information will be provided to all study participants in case of an adverse event. Subject records will be maintained on a password-protected computer or in a locked file, and a study-assigned identification number will be used in lieu of the subject's name or personal identifiers on data summary sheets.

9.2 Subject Consent:

A consent form has been developed that describes the nature of the research, the risk/benefit ratio, and the voluntary nature of subject involvement. Consent will be obtained directly from the participant in a private location within the clinic by the study PI, study coordinator, or other study staff. Potential subjects will be given a verbal explanation of the research and then will be granted ample time to read the consent form or have the consent read to them if necessary, and permitted to ask questions. Subjects unwilling to provide signed consent will not be enrolled.

9.3 Risks and Benefits:

As both arms of this study are consistent with current standard-of-care practices, we do not anticipate any increase in rates of complication compared to the reported rates in published literature.

9.4 Discomforts and Inconveniences:

The expected discomforts and inconveniences are related to the placement of a Baerveldt or ClearPath implant and the time required in the standard-of-care post-operative follow up. Participation in this study is not expected to add any significant discomfort and/or inconvenience to the subject as the study interventions and follow-up schedule are utilized in current standard of care post-operative management.

9.5 Discontinuation of Treatment and Withdrawal of Subjects

The reasons why a subject may discontinue or be withdrawn from the study include, but are not limited to, adverse effects, subject request, investigator request, protocol violation and lost to follow-up.

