3.0 INTRODUCTION

3.1 Background

Implanting aqueous drainage devices has become an increasingly common surgical treatment for glaucoma. Medicare data between 1995 and 2004 demonstrated a steady increase in the use of these devices.^{1,2} Even with the advent of minimally invasive glaucoma surgery (MIGS), aqueous drainage devices is still a mainstay of treatment for uncontrolled intraocular pressure (IOP).³ Currently, one of the most common aqueous drainage devices used is the Baerveldt implant (Johnson & Johnson, Vision, Jacksonville, Florida) (Figures 1&2).

[figure not shown]

Figure 1. Schematic of the different Baerveldt Implant Models available. On the far most right is the Baerveldt 101-350 model that will be utilized in this study.

[figure not shown]

Figure 2. Depiction of typical Baerveldt implant once positioned and implanted on the eye.
www.towerclockeyecenter.com

The Baerveldt implant is an FDA-approved silicone, non-valved implant. This device comes in 3 variants: a single 250 mm² model and two 350 mm² models (Figures 1&2). For the purposes of this study, we will be focusing on the Model BG-101-350, (Figures 1&2) which will be the only variant of the Baerveldt evaluated in this study. As it is non-valved, it needs early restriction of fluid flow to minimize hypotony while the eye forms a fibrous capsule around the implant. One common way of restricting fluid flow is by ligating or tying off the Baerveldt tube with an absorbable suture that dissolves by post-operative week 4 to 6. For better control of the tube opening and intraocular pressure reduction during the post-operative

period, many surgeons place a suture within the lumen of the implant, called a ripcord, at the time of surgery. This ripcord suture is accessible at the slit lamp in clinic.

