5.0 STUDY DESIGN AND METHODS

5.1 Experimental Design

This is a randomized prospective study of post-operative surgical outcomes and complication rates in patients with a Baerveldt 350 implant vs the Ahmed ClearPath implant. Each subject will be randomized to the Baerveldt group or ClearPath group at the time of consent for the study. A baseline eye exam will be conducted as per the study flowchart (Section 2). Surgeons will include

- [name]
- [name]
- [name]
- [name]
- [name] [name]
- [name]
- [name], PhD
- [name], PhD
- [name]
- [name]
- [name]
- [name], PhD
- [name]
- [name]

It will not be possible for the surgeon to be masked given that s/he will be implanting the device. The subject will then be seen on post-operative day 1 (± 1 day), week 1 (± 5 days), week 4 (± 1 week), week 6 (± 1 week), month 3 (± 1 week), month 6 (± 2 weeks) and year 1 (± 1 month) as per the standard-of-care post-operative schedule. At each of these post operative visits, ophthalmic exams will be conducted, collecting data such to be in accordance with the study flowchart (Section 2).

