8.1 Statistical Considerations

8.1.1 Analysis Plan

The Intent-To-Treat (ITT) population includes all randomized subjects who had at least one post-op assessment. The primary efficacy analysis will be performed on the ITT population with Last Observation Carried Forward (LOCF). If a subject is deemed to have a failed surgery and undergoes a rescue procedure, the last observation collected prior to the intervention will be used for efficacy analyses at all later timepoints.

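### Section 9.5 does not separate withdrawal for adverse effects, investigator request or protocol violation from the end of data collection, so LOCF can replace Year 1 IOP that could often still be measured

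*Combined protocol and SAP*

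**What the plan says.** Section 9.5 is a single sentence. It opens "The reasons why a subject may discontinue or be withdrawn from the study" and gives an open-ended list: "adverse effects, subject request, investigator request, protocol violation and lost to follow-up". The heading names both stopping treatment and withdrawing subjects, but the text does not distinguish them. It sets no criteria and does not say who decides. No other section asks for outcome data after a withdrawal.

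Four other parts of the plan bear on this:

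- **Analysis (8.1.1).** The ITT set is every randomized subject with one or more post-operative assessments. The primary efficacy analysis fills missing values by LOCF.
- **Visits (5.1, 7.0, 9.4).** Subjects are seen "as per the standard-of-care post-operative schedule", and the study procedures are described as standard of care.
- **Early flow restriction (3.1).** A common method is to tie off the Baerveldt tube with an "absorbable suture that dissolves by post-operative week 4 to 6". The ClearPath is said to need early restriction for the same reasons.
- **Masking (5.1, 5.6).** For the operator: "It will not be possible for the surgeon to be masked given that s/he will be implanting the device". For the subjects: "Study subjects will be masked as to which implant they will receive".

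The null hypothesis in 8.1.2 covers complication rates as well as IOP.

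**The concern.** The randomized intervention is one operation. Once it is done, withdrawing a subject from the study mainly ends the recording of outcomes. Adverse effects, a protocol violation or an investigator's request do not make the Year 1 pressure unmeasurable, and the patient would normally still attend clinic. As written, 9.5 allows the trial to stop recording that subject and 8.1.1 then fills in the gap.

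Three things are at stake:

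- **IOP.** A value carried from day 1, week 1 or week 4 may describe a tube that is still restricted, not the device at Year 1.
- **Complications.** Withdrawal for adverse effects stops observation in the subjects who are having them, although complications are part of the hypothesis.
- **Failure and Year 1 measures.** The pressure-based failure criteria in section 3.2 need two consecutive visits after three months, so a subject withdrawn before then cannot meet them. Quality of life is scheduled only at Year 1 (section 2.0), so LOCF has nothing to carry.

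Missing data of this kind are avoidable and may be informative.

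**Working it through.** **1. The plan's own figure.** Inputs from 5.3 and 8.1.3: difference 2 mmHg, SD 5.9 mmHg, two-sided alpha 0.05, power 80%, dropout 10%.

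n per group = 2 × [5.9 × (1.960 + 0.842) / 2]² = 136.6. Dividing by 0.9 gives 151.8, which rounds up to 152. (Rounding to 137 before inflating gives 153.) The stated 152 per group is reproduced, so the sample size is not in dispute. The 10% allowance does not split discretionary withdrawal from loss to follow-up, and adding subjects does not remove bias.

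**2. What happens to a withdrawn subject.** Reading 9.5 with 8.1.1:

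| Time of withdrawal | In the ITT set? | Year 1 IOP used |
|---|---|---|
| After randomization at consent, before any post-operative assessment | No | None |
| After one or more post-operative assessments | Yes | Last reading carried forward |

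No text removes protocol violators who have a post-operative assessment.

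**3. Bias formula.** Let p be the share of an arm withdrawn in this way. Let g be the average error of the carried value, that is, the carried IOP minus what the same subjects would have had at Year 1. The shift in the between-arm difference is p₁g₁ − p₂g₂. If g is the same in both arms, this is f × g, where f = p₁ − p₂. If p and g are both equal across arms, it is zero.

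**4. Illustration.** The documents give neither f nor g, so both are assumptions. With 152 per arm, f of 2% to 10% is about 3 to 15 subjects (0.02 × 152 = 3.0; 0.10 × 152 = 15.2).

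| Excess f | g = 2 mmHg | g = 5 mmHg | g = 10 mmHg |
|---|---|---|---|
| 2% | 0.04 | 0.10 | 0.20 |
| 5% | 0.10 | 0.25 | 0.50 |
| 10% | 0.20 | 0.50 | 1.00 |

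As a share of the 2 mmHg target, the range runs from 0.04/2 = 2% to 1.0/2 = 50%.

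**5. Effect on the test.** LOCF keeps the nominal n, so SE = 5.9 × √(2/152) = 0.677 mmHg. With bias b and no true difference, the two-sided type I error is Φ(−1.96 − b/SE) + 1 − Φ(1.96 − b/SE):

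| Bias b (mmHg) | Type I error |
|---|---|
| 0.10 | 5.3% |
| 0.25 | 6.6% |
| 0.50 | 11.4% |
| 1.00 | 31.5% |

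**The case against.** The strongest defence is that 9.5 is a short descriptive list of ways in which subjects may leave. It does not require anyone to be withdrawn. Harm needs the discretion to be used, and between-arm bias under no true difference also needs withdrawal or LOCF error to be unequal between arms. Both arms share one visit schedule, and section 3.2 expects the devices to perform alike. The substitution itself comes from LOCF in 8.1.1, which applies equally to consent withdrawal and loss to follow-up. All of this stands, and it limits the size that can be claimed. It does not remove the gap: the rule as written permits obtainable data to be dropped.

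A reader might infer four stronger things that the documents do not support:

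- **That 9.5 defeats the ITT analysis.** Subjects with a post-operative assessment stay in the set. Those withdrawn before one are excluded by the definition in 8.1.1 acting together with 9.5.
- **That unmasked people decide on withdrawal.** Only the surgeon is stated to be unmasked, and 9.5 names no decision-maker. Investigators recruit from their own clinics (6.1), and surgeons and their staff monitor safety (9.1). It is therefore a reasonable inference that the surgeon would decide, but it is not a stated fact.
- **That withdrawals are likely to differ by device.** Nothing in the documents shows this.
- **That the bias can be sized by setting an assumed high early pressure against the 13.6 mmHg Year 1 mean.** The documents give no early IOP. The relevant comparison is with the same subject's own Year 1 value, not a group mean. The error could also go either way: section 3.1 names hypotony as the early risk of a non-valved implant, and section 7.2 lets medication be added at any time.

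It would also be too strong to say that nothing remains to be discontinued after surgery, since device removal is a listed failure criterion.

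**Conclusion.** The point holds in a limited form. Section 9.5 allows withdrawal from the study for reasons that need not prevent outcome measurement, and no section keeps data collection going afterwards. With LOCF, this can replace obtainable Year 1 IOP with readings that may predate tube opening, and it can cut short the record of complications. The ITT comparison is undermined, not defeated.

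The size is unknown. The range of 0.04 to 1.0 mmHg is an illustration that rests on assumed values of f and g. Its upper end is severe, because a 10-point excess in one arm equals the plan's whole dropout allowance. The change is worth making because the loss is avoidable and the remedy is cheap.

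**What to change.** Amend 9.5 to separate leaving treatment from ending data collection, and state that:

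- adverse effects, protocol violation or an investigator's decision do not end outcome data collection;
- IOP and complications are collected to Year 1 for every randomized subject unless consent is withdrawn or the subject is lost;
- the observed values are analysed in the randomized arm;
- the reason and date of each withdrawal are recorded and reported by arm.

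This concerns data collection only and leaves clinical decisions untouched. It does not cure LOCF for subjects who withdraw consent or are lost. A sensitivity analysis not based on LOCF would show how much those cases matter.

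The cost is protocol wording, an IRB amendment (section 11.0) and some extra data entry, since the visits are already standard of care. The sample size of 152 per group does not change.
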